## 2. Fiberoptic Evaluation of the SGADs Anatomical Position

Once ventilation is achieved, the laryngeal view will be determined, thus illustrating the anatomical positioning of the device. The investigation will be performed with the aid of the flexible scope, the Ambu aScope3 Slim, which will be introduced into the airway tube and guided through the SGAD until it is possible to view the vocal cords. Description of the maximal optical view will be measured by the Percentage Of Glottic Opening (POGO). The POGO score and any presence of blood will be recorded.

If the epiglottis is down-folded obscuring the optical view, a jaw lift will be performed and another POGO score will be obtained. In case of secretions or blood, the channel of the aScope3 Slim will be used for removing the debris. If this fails, the aScope3 Slim will be withdrawn and a suction catheter will be used, and the lens of the aScope3 Slim will be cleaned using an alcohol wipe, before a new attempt is commenced.

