### **2.0 Objectives and Hypothesis**

The purpose of this study is to estimate the ratio or difference in success rate of both the Ambu® AuraGain™ and Teleflex® LMA Protector™ during insertion and placement into an airway. Other findings include ease of supraglottic airway device (SGAD) insertion, anatomical fit of the SGAD (i.e. SGAD displacement, bloodstaining), rate of successful ventilation and intubation, functionality of gastric drainage channel (via orogastric tube insertion through each SGAD; to ensure easy insertion), oropharyngeal leak pressure (OLP; measured by a portable, handheld manometer), and postoperative complications in elective surgical patients who are not expected to have a difficult airway. Also, a fiberoptic assessment (with the Ambu® aScope™ 3 Slim) of the glottic view via the SGAD device and signs of airway morbidity will be investigated.

**2.1 Primary:** The ratio or difference in success rates of either the Ambu® AuraGain™ or Teleflex® LMA Protector™ during insertion and placement into an airway.

**2.2 Secondary:** Rate of successful ventilation and intubation (by utilizing the SGAD as an intubation conduit guided by the Ambu® aScope™ 3 Slim), ease of SGAD insertion (based on a numerical subjective rating scale), anatomical fit of SGAD (i.e. SGAD displacement, bloodstaining), OLP (measured by a portable, handheld manometer), functionality of gastric drainage channel which will be inserted through the appropriate channel of the SGAD, and postoperative complications

**2.3 Exploratory:** Fiberoptic assessment of the glottic view via the SGAD device and signs of airway morbidity

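### POGO is offered as evidence of device position but is scored as the best view from no fixed point on the device, so it may partly reflect how the scope was handled

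*Combined protocol and SAP*

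**What the plan says.** Section 8.0, under the heading on fiberoptic evaluation of anatomical position, states the purpose: "Once ventilation is achieved, the laryngeal view will be determined, thus illustrating the anatomical positioning of the device". The scope is to be "introduced into the airway tube and guided through the SGAD until it is possible to view the vocal cords". What is scored is the best view: "Description of the maximal optical view will be measured by the Percentage Of Glottic Opening (POGO"). The data listed are brief: "The POGO score and any presence of blood will be recorded". Scope depth and tip position are not listed there.

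One finding triggers a second score: "If the epiglottis is down-folded obscuring the optical view, a jaw lift will be performed and another POGO score will be obtained". The plan does not say which of the two scores is analysed.

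Section 2.3 ranks this assessment as exploratory: "Fiberoptic assessment of the glottic view via the SGAD device and signs of airway morbidity". The secondary endpoint in section 2.2 that deals with seating is defined differently: "anatomical fit of SGAD (i.e. SGAD displacement, bloodstaining").

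Section 3.0 describes the scope tip as steerable, with a bending angle of 130°/130°. Section 8.0 says that 8 study anesthesiologists take part. No blinding of the person who scores the view is described.

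**The concern.** A view through a device shows where the device sits only if the viewpoint is fixed to the device. Here the scope stops when a result is reached (cords visible), and the best view obtained is then scored. Suppose one device is well seated and another is somewhat displaced. The first shows the glottis from its outlet. The second may show it only after the tip has been advanced or angled. Under the text as written both can receive a similar score, although they sit differently.

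The person steering can see which device is in place, and several anesthesiologists take part. How far the tip is moved can therefore vary by operator and, without intent, by device. At stake is whether the POGO comparison can be read as a comparison of seating, which is the use the section gives it.

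**Working it through.** **1. Figures in the plan.** The only design calculation is in section 11.0: a 95% interval of (0.945, 1.255) for the ratio of first-attempt success rates, with 0.90 and 0.98 and 25 patients per arm. It reproduces:

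- SE = √[(1−0.90)/(25×0.90) + (1−0.98)/(25×0.98)] = 0.0725
- exp(ln(0.98/0.90) ± 1.96×0.0725) = 0.9446 to 1.2552

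This concerns the primary endpoint and does not involve POGO. Sections 10.0 and 11.0 give no mean, SD or expected difference for POGO, so the size of any effect can only be illustrated.

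**2. Purpose against rule.**

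| Element | What the text fixes |
|---|---|
| Purpose | Position of the device |
| Where the scope tip stops | When the cords can be seen |
| View that is scored | The maximal one |
| Landmark on the device | None named |
| Limit on advancing or steering | None stated |
| Scope depth or tip position recorded | Not listed in this section |
| Score analysed when there are two | Not stated |

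Elsewhere section 8.0 does define such points. An insertion attempt starts at the lips, a gastric tube attempt at the proximal channel, and an intubation attempt at the SGAD connector.

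**3. Illustration of size.** All inputs are assumptions. POGO at the device outlet follows a beta distribution with concentration 2 and mean m = 0.75 in one arm and 0.55 in the other, so the true gap is 20 points.

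- SD = √[m(1−m)/3], which is √(0.1875/3) = 25 points and √(0.2475/3) = 29 points.
- If scope handling lifts every view to at least T, the recorded score is max(POGO, T). Its mean is T + ∫ from T to 1 of P(POGO > x) dx.

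| Floor T | Mean, arm A | Mean, arm B | Gap (points) |
|---|---|---|---|
| none | 75.0 | 55.0 | 20.0 |
| 20% | 75.3 | 56.5 | 18.9 |
| 30% | 75.9 | 58.4 | 17.5 |
| 60% | 80.6 | 70.0 | 10.6 |
| 80% | 87.4 | 82.7 | about 4.7 |

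If only a random half of patients in each arm is affected, the gap is the average of 20 and the tabulated value: (20 + 10.6)/2 = 15.3 at a floor of 60%, and (20 + 4.75)/2 = 12.4 at 80%, where 4.75 is the unrounded gap.

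**4. Unequal handling.** The table assumes the same handling in both arms. If views were lifted to 60% in arm B only, the gap would be 75.0 − 70.0 = 5.0. If in arm A only, it would be 80.6 − 55.0 = 25.6. Equal handling shrinks the difference in this model, whereas unequal handling can shrink or enlarge it.

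**The case against.** The strongest reply is that the text need not be read as permitting a search for a better view. Guiding the scope through the device, under a heading about the device's position, can be taken to mean a view from inside the device or at its exit. The section does not mention going beyond the outlet. The separate intubation step does take the scope further and says so, naming the carina as the end point. This stands in part. The wording is ambiguous and does not prescribe a biased method, but the only stopping point it states is sight of the cords.

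A reader might infer that low scores are ruled out, or that both arms are bound to sit near the ceiling. The documents do not support this. A partial view of the cords meets the stopping rule and can score low. The word *another* in the jaw-lift sentence implies a score taken while a down-folded epiglottis still obscures the view, so that form of malposition leaves a trace. The high floors in the illustration are assumptions, and a floor of 20–30% costs only one to three points of the gap.

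A reader might also infer that the trial's conclusions on success or fit are compromised. They are not. The glottic view is exploratory, the primary endpoint is first-attempt success, and the secondary fit endpoint rests on displacement and bloodstaining. Tooth-mark position, the capnography trace, leak pressure and gastric tube passage also bear on seating or seal.

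Finally, section 5.0 refers to a CRF in Appendix C that is not in the text reviewed. A fixed scoring point there cannot be excluded. If one exists, section 8.0 should state it.

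**Conclusion.** The concern holds in a limited form. The plan presents the fiberoptic view as showing device position, but it scores the best view from a viewpoint not tied to the device. POGO may therefore partly measure scope handling by an unblinded operator, and the exploratory comparison may be blunted or biased.

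How much is unknown. With an assumed true gap of 20 points and equal handling in both arms, what remains runs from about 17–19 points (floor of 20–30%) through 10.6 (60%) to about 4.7 (80%). These figures rest on the assumed beta distributions and on every view being lifted to the floor. They show how the gap depends on scope handling and do not predict what will be observed. The documents do not show that operators will in fact steer for a better view. The point merits a change because the remedy is cheap and because a view from the outlet that was not recorded cannot be recovered later.

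**What to change.** In section 8.0 and on the CRF:

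- Record POGO in both arms with the scope tip at the distal end of the SGAD airway tube, before any advance, steering or jaw lift.
- Name this score as the one used for the between-device comparison.
- Record the best view, after advancing or jaw lift, as a separate item.

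This also settles which score is analysed when a jaw lift leads to a second one. The cost is a sentence or two of text and one extra CRF field, within the same scope pass. The downside is that reported scores will be lower than best-view scores, and the report should say so.

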## 3. Investigation of the Functionality of the Gastric Drainage Channel of the SGADs

A size 16 Fr. gastric tube will be pre-lubricated with a water-soluble lubricant and will be passed through the gastric drainage channel, of either SGAD, until depth mark of 40-50 cm. The female gastric drainage channel will be used on the Protector. Confirmation of gastric tube placement will be obtained by aspiration of 2 ml of gastric content and/or auscultation of inflated air at the epigastrium.

An insertion attempt is defined as when the tip of the gastric tube touches the proximal channel. Insertion failure is defined as inability to pass a gastric tube until appropriate depth mark, lack of confirmation of correct placement by auscultation, and inability to evacuate any gastric content.

Additionally, the ease of insertion of gastric tube, number of insertion attempts, volume of air evacuated, volume of gastric content, and fluid observed in gastric drainage channel will be recorded.

## 4. Measurement of Oropharyngeal Leak Pressure (OLP)

The measurement of OLP will be performed, with an Ambu cuff pressure gauge, prior to surgical incision and at the end of surgery; this measurement will be performed by closing the adjustable pressure-limiting valve, with a fresh gas flow of 3 L/min, and noting the airway pressure at equilibrium. The maximum pressure allowed is 40 cmH2O. The epigastrium will not be auscultated when measuring leak pressure with the purpose of detecting any possible air entrainment into the stomach intraoperatively. Moreover, OLP and any audible leak into the stomach or over the mouth will also be recorded.

## 5. Use of SGAD as an Intubation Conduit

### 1) Intubation Procedure

An intubation procedure will be performed by placement of an ETT over the Ambu aScope3 Slim. A standard use Parker Flex Tip™ ETT of maximum recommended size will be used depending on SGAD size for both female and male patients. ETTs of 6.0, 7.0, and 8.0 mm will be paired with the AuraGain, sizes 3, 4, and 5 respectively. An ETT of 6.0 mm will be paired with the LMA Protector size 3, and ETTs of 7.0 and 8.0 mm will be paired with the LMA Protector, sizes 4 and 5 respectively. The airway tube of the SGAD will be lubricated and the aScope3 Slim will be passed through the airway tube until carina is visualized. Once the aScope3 Slim is at the carina, the ETT will be passed down the insertion cord of the aScope3 Slim and correct placement of the ETT will be verified. Once the ETT is placed correctly, the cuff of the ETT will be inflated and the aScope3 Slim will be removed.

An intubation attempt will be defined as from when the tip of the ETT is touching the SGAD connector and advanced through the SGAD. If an unsuccessful attempt occurs, and the ETT is withdrawn from the SGAD, the next attempt will be considered a new attempt. No more than 3 intubation attempts shall be made for proper ETT placement. If unsuccessful after 3 attempts with at least 2 different size SGAD devices used, standard tracheal intubation will be performed.

Intubation time will be measured from when the tip of the aScope3 Slim is touching the SGAD connector until endoscopic confirmation of correct ETT placement. End-tidal capnography will be used to confirm successful intubation. In addition, size of SGAD, size of ETT, and number of intubation attempts will also be recorded. Qualitative assessment of ease of intubation, and will be based on an analog scale from 1-4: 1: Easy 2: Resistance 3: Difficult 4: Unsuccessful.

## 9.0 Risks and Benefits

### Risks

In general, subjects will be a part of a study that may potentially affect how anesthetic providers practice and manage difficult airway patients. As a specific benefit, subjects will be intubated using a new video laryngeal mask airway. Risks are similar to a regular laryngeal mask airway, including but not limited to, device malfunction and airway adverse events.

As with use of all medical devices, complications may occur. Recognized risks associated with the use of the study intervention include, but are not limited to, the following:

- Allergic reactions: although the materials being used are hypoallergenic and the risk is small, there remains a risk for an allergic reaction that may result in hives, swelling, or anaphylaxis.
- Oropharyngeal injury: although the both LMA were designed for supraglottic placement, some bleeding/bloodstaining may occur upon placement
- Oropharyngeal pressure: over inflation of the both LMA can occur that can cause an increase in pressure

#### Risk Minimization

- To minimize the risk of allergic reactions, both Auragain and LMA Protector have undergone and successfully passed biocompatibility testing.
- To minimize the risk of an oropharyngeal injury, it is recommended that all clinicians be properly trained on how to use the both LMAs and be familiar with the Instructions For Use (IFU).
- To minimize the risk of increased pressure, it is recommended that all clinicians be properly trained on how to both LMAs and the recommended inflation pressure. There will also be a recording of the both LMA cuffs when inflated measured by the OPL testing, to aid in adequate cuff inflation.

#### Potential Benefits to Subject

- Improved oxygen delivery, administration, and oxygenation
- Potentially able to reduce post-op respiratory complications

#### Alternatives to Participation

The alternative for not participating in this study would result in not using either SGAD for tracheal intubation. Therefore, a traditional alternative (the standard of care) such as a laryngoscope would be utilized for tracheal intubation.

### 10.0 Statistical Methods

Descriptive statistics such as the mean (standard deviation) or median (range) will be used to summarize continuous variables as appropriate. Frequencies and percentages will be used to summarize categorical variables, such as success rates. Independent samples t-tests or Wilcoxon rank-sum tests (if more appropriate) will be used to compare differences in continuous variables between study arms. Fisher's exact test or Chi Square test will be used to compare categorical variables between study arms. Correlations and regression will be used to estimate associations of interest, primarily for exploratory analyses and further hypothesis generation.

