## **5.0 Randomization**

CORe will be the designated software for the randomization of each intervening device (SGAD) arm. The treatment will be named 1 for Ambu® AuraGain™, 2 for Teleflex® LMA Protector™ for both parts of the study in the list. Block randomization is 25 blocks of size of 2.

The following demographic data and medical history will be collected on the case report form (CRF): Gender, age, height, weight, body mass index, fasting time, ASA class, Mallampati classification, thyromental distance, sternal distance, interincisor distance, and ability to protrude lower jaw. Please refer to Appendix 'C'.

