### 11.0 Sample Size

The AMBU® AURAGAIN™ and TELEFLEX® LMA PROTECTOR™ are FDA approved SGADs that can be used for ventilation, and as a conduit for intubation. For patients in the general hospital setting, each device has exhibited a relatively high success rate of at least 90% as a ventilatory device. Success is defined as the insertion and placement of a SGAD on the first attempt. Success rates will be computed as proportions for each study arm. Taking the ratio of the success rates for each study arm will derive the relative risk. A two-sided 95% confidence interval will have the following lower and upper limits: (0.945, 1.255) assuming a relative risk of 1.089 (ie. success rate for study arm 1 = 0.90 and success rate for study arm 2 = 0.98) and 25 patients in each treatment arm.

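### Section 10.0 does not carry forward the relative risk with 95% CI that Section 11.0 is built on. It leaves the test for first-attempt success open, and the interval method behind Section 11.0 is a poor one at these rates.

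*Combined protocol and SAP*

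**What the plan says.** Section 2.0 states an estimation aim: "The purpose of this study is to estimate the ratio or difference in success rate". Section 2.1 repeats it as the primary objective and leaves the scale open: "The ratio or difference in success rates of either the Ambu® AuraGain™ or Teleflex® LMA Protector™ during insertion and placement into an airway".

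Section 11.0 is more specific. It defines the endpoint ("Success is defined as the insertion and placement of a SGAD on the first attempt"), says that the ratio of the two success rates gives the relative risk, and reports an expected two-sided 95% interval of 0.945 to 1.255, "assuming a relative risk of 1.089" ("success rate for study arm 1 = 0.90 and success rate for study arm 2 = 0.98") and "25 patients in each treatment arm". It does not name the interval method.

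Section 10.0, the analysis section, uses success rates as its example of a categorical variable. They are to be summarised by counts and percentages, and "Fisher's exact test or Chi Square test will be used to compare categorical variables between study arms". It gives no rule for choosing between the tests, no continuity-correction statement, no significance level, no effect measure and no interval.

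**The concern.** The quantity the trial is planned around, a relative risk with its interval, is missing from the section that says how the data will be analysed. What stands there for the primary endpoint is an open choice between two tests that give only a p-value. With success rates this high, the expected failures are 25 × 0.10 = 2.5 and 25 × 0.02 = 0.5 per arm, and the choice of test or interval method can change the headline.

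Two things are at stake. First, the same data could be reported as a difference or as no difference, depending on a choice made after the results are seen. Second, if the method implied by Section 11.0 is used, the reported interval will be too narrow for its stated confidence level, and in some trials it will have no width at all.

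**Working it through.** **Inputs.** n = 25 per arm (Section 11.0; Section 5.0 agrees: "Block randomization is 25 blocks of size of 2"). Success rates p1 = 0.90 and p2 = 0.98, ratio 0.98/0.90 = 1.089, two-sided 95% (Section 11.0). Assumed: a two-sided 0.05 level for the tests, to match the 95% interval, and independent binomial counts. The rates 0.80 v 0.98 are an added sensitivity case, not a plan figure.

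**1. The plan's interval reproduces as log-Wald.** SE(log RR) = √[(1−p1)/(n·p1) + (1−p2)/(n·p2)] = √[0.10/22.5 + 0.02/24.5] = 0.0725. Limits: 1.0889 × exp(±1.96 × 0.0725) = 0.945 and 1.255, as stated.

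**2. Rejection rates of the permitted tests.** All 26 × 26 possible tables were enumerated, each weighted by its binomial probability, counting p ≤ 0.05.

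| True rates | Fisher's | Chi-square, uncorrected | Chi-square, Yates |
|---|---|---|---|
| 0.90 v 0.98 | 2.3% | 15.3% | 2.1% |
| 0.80 v 0.98 | 30.3% | 58.9% | 26.9% |
| 0.90 v 0.90 | 0.9% | 4.9% | 0.6% |
| 0.94 v 0.94 | 0.2% | 2.8% | 0.1% |

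At the planning rates, Fisher's and uncorrected Chi-square reach different conclusions in 13.0% of trials.

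**3. One plausible table, 21/25 v 25/25.**
- Fisher's: p = 0.110.
- Uncorrected Chi-square: 50 × (21×0 − 4×25)² / (25×25×46×4) = 4.348, p = 0.037. With Yates correction, p = 0.118.
- Log-Wald: RR = 25/21 = 1.19, SE = √(1/21 − 1/25) = 0.0873, interval 1.003 to 1.413, which excludes 1.
- Newcombe interval for the 16-point difference: −0.4 to +35 points, which includes 0.

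Across all tables at the planning rates, the log-Wald interval and Fisher's test disagree in 12.3% of trials.

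**4. Coverage of the interval for the ratio, same enumeration.**

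| True rates | Log-Wald | Score |
|---|---|---|
| 0.90 v 0.98 | 92.4% | about 97% |
| 0.80 v 0.98 | 89.8% | 95.6% |

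The 0.98 arm has no failures with probability 0.98^25 = 60%. Both arms have none with probability (0.90 × 0.98)^25 = 4.3%. The log-Wald interval then runs from 1 to 1 and counts as a miss. These tables supply 4.3 of the 7.6 points of non-coverage at the planning rates. At 0.80 v 0.98 they are rare, (0.80 × 0.98)^25 = 0.2%, so the shortfall there has another source.

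**5. What the plan's interval becomes.** At the same expected counts (22.5 and 24.5 successes), the score interval for the ratio is about 0.91 to 1.36, a width of 0.45 against 1.255 − 0.945 = 0.31. The Newcombe interval for the 8-point difference is about −8 to +26 points.

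**6. What a score interval does not do.** At a ratio of 1, the squared score statistic equals the uncorrected Chi-square. For 21/25 v 25/25 that is 4.348 (or 4.348 × 49/50 = 4.26 with the Miettinen-Nurminen factor), above 3.84. The score interval therefore also excludes 1 while Fisher's p is 0.110. A better interval improves coverage. Only a choice made in advance removes the conflict with Fisher's test.

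**The case against.** The case against has several parts.

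- **The plan already names an estimate and an interval.** This is right, and a reader who infers from Section 10.0 alone that no ratio is planned would be wrong. Section 11.0 names the relative risk and sizes the trial on its interval. What remains is that Section 10.0 does not adopt it, Section 2.1 leaves ratio or difference open, and no interval method is named.
- **The trial plans no power or formal test, so rejection rates are beside the point.** This is partly right. No hypothesis test is declared primary, and the expected interval openly includes 1. But Section 10.0 does commit to comparing categorical variables by a test, with success rates as its example, so a p-value for the primary endpoint will be produced.
- **By custom, Fisher's is used when an expected count is below 5.** That rule would pick Fisher's in more than 99.9% of trials at the planning rates and would reject in 2.3%. The plan does not state it, and it would not settle the conflict with the log-Wald interval.
- **The 2% v 15% contrast depends on the uncorrected statistic.** This is true. With Yates correction it nearly vanishes (2.3% v 2.1%). Which version is meant is one more unstated choice.
- **Chi-square is not faulty here.** This also stands. It is tempting to infer from the small expected counts that it gives false positives, but its rejection rate under equal rates is 4.9% at 0.90 and 2.8% at 0.94.
- **No test cures the low rejection rate.** This is true. The cause is 25 patients per arm. The point concerns how the result is estimated and reported, not power.

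**Conclusion.** The concern holds in this form: the primary analysis is not fixed in Section 10.0, and the interval method that Section 11.0's figures imply performs poorly at the rates the plan expects. The size is a 13.0% chance at the planning rates that two permitted tests disagree, a 12.3% chance that Fisher's test and the log-Wald interval disagree, and log-Wald coverage of about 92% (90% at 0.80 v 0.98) against a nominal 95%.

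This rests on a two-sided 0.05 level, on the uncorrected Chi-square for the 15.3% and 13.0%, and on log-Wald being the intended method. That last assumption is inferred from the match of 0.945 to 1.255, because the plan does not say so.

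The documents do not support reading this as an absent effect measure or as an invalid Chi-square test. They also contain no claim that the devices perform equally. The wording proposed on that point is a safeguard, since a non-significant Fisher's test is close to certain at the planned 8-point difference. The change should be made before data are seen. It concerns the validity of the reported interval and the fixing of the analysis, and does not call for redesign.

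**What to change.** In Section 10.0:

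1. Name one primary analysis: the relative risk of first-attempt success with a two-sided 95% score-type interval. Align Section 2.1 with it.
2. Give the risk difference with a Newcombe or Miettinen-Nurminen interval as supportive, and say that the primary interval governs if the two point different ways.
3. Fix in advance one test, if any, for the primary endpoint, including whether a continuity correction applies. If Fisher's is kept, say that it may disagree with the interval and that the interval governs.
4. State that p > 0.05 will not be read as equal performance.

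In Section 11.0, restate the expected interval by the same method (about 0.91 to 1.36) and name the method.

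**Cost.** A few lines and standard software, with no extra patients. The stated interval becomes wider, and the freedom to choose the test later is lost. Keeping the ratio as primary respects the measure that Section 11.0 already uses. If the sponsor prefers the difference, that is acceptable, provided one scale is fixed beforehand.
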